6.5.3 Post-treatment care

The subject should avoid excessive sun, UV lamp exposure and extreme temperature until any initial swelling and redness has resolved.

The subject should be asked to avoid touching or shaving the treated area and not to apply any creams or cosmetics in the treated area before the skin has healed completely in order to prevent infections or elicit an inflammatory reaction. The subject should also be reminded to abstain from prohibited medications, treatments, and procedures.

A subject diary will be handed out after each treatment session, and the subject should be reminded to record all expected symptoms in the treated area.

Detailed information regarding the post-treatment care and patient instruction is provided in the study IFU.

6.5.4 Post-trial provisions

In time, the implant will be degraded in the body and additional treatments will be necessary to maintain the aesthetic result.

7.3 Global Aesthetic Improvement Scale (GAIS)

The 7-graded GAIS will be used to live assess the aesthetic improvement of cheek wrinkles by the Treating Investigator and the subject, by comparing to a photograph taken at the baseline visit before the first treatment. The Treating Investigator and the subject will, independently of each other, respond to the question: "How would you describe the aesthetic improvement today compared to the photograph taken before treatment?" by using the respective categorical scale below.

[figure not shown]

7.4 Subject Satisfaction Questionnaire

Subject satisfaction with treatment result will be assessed using a subject satisfaction questionnaire.

[figure not shown]

MA-39953

7.5 FACE-Q "Satisfaction with Cheeks"

Subject satisfaction will be assessed using the "Satisfaction with Cheeks" FACE-Q questionnaire.

7.6 Lifting effect of cheek using 3D imaging

Lifting effect of cheek will be assessed using 3D camera and software. Camera equipment will be provided by the Sponsor or their designee. Further details regarding 3Dphotography procedure will be specified in a separate user guide. Site should follow the maintenance instructions from the equipment manufacturer and keep records of maintenance in the investigator file.

7.7 Return to social engagement

Subjects will record the date and earliest time he/she felt comfortable to return to social engagement following treatment in a subject diary. Return to social engagement is defined as making public/social appearances, including but not limited to returning to work at a business office or other public work place; having dinner in a public restaurant; attending a social event/gathering such as dinner party, etc. Subjects will record the time they feel comfortable (with or without covering make-up) resuming social interactions, not necessarily the time for their first social interaction.

Subjects will be asked to complete the following questions in the subject diary:

Did you feel comfortable to return to social engagement today?

Yes or No

If yes, what was the earliest time you felt comfortable to return to social engagement?

[figure not shown]
Record Date and Time (using 24-hour clock)

7.8 Ultrasound

Dermal thickness will be assessed using ultrasound, a select number of sites will conduct the assessment. Ultrasound equipment will be supplied by the sponsor to sites. Further instructions regarding the equipment and procedure will be specified in a separate user guide.

7.9 Radiance, skin tightness and jawline contour assessment

The Treating Investigator will assess skin radiance, skin tightness and jawline contour after treatment based on review of baseline photographs and live assessment by responding to the following questions:

7.10 Photography

Photographs shall be taken at the time points indicated in the Schedule of Events. For those randomized to treatment, this should occur prior to the first injection of the study product and before each additional treatment. Camera equipment will be provided by the Sponsor or their designee and standardized photographs should be taken. Instructions for photography are provided in a separate photography manual. Baseline photographs may be used as a reference in the assessment of GAIS by the Treating Investigator and subject. Photographs may also be taken to document AEs at the Treating Investigator's discretion. Personnel will be trained in the photographic equipment and technique before the study start.

7.11 Improvement in cheek wrinkles by Central Independent Reviewer

Improvement in cheek wrinkles will be assessed by a Central Independent Photographic Reviewer by comparing random blinded pairs of photographs of the baseline visit and the follow-up visits at month 12. The photos from the follow up visits will include subjects from both the treatment and no treatment group in a blinded fashion. The reviewer will answer the question "Which photo represents post treatment" by responding right, left or neither photo.

8 Safety Assessments

Safety assessments for this study include an evaluation and an interview of the subjects at each visit to obtain information about any medical occurrence that meets the definition of an AE, a subject diary, laboratory tests, Cheek firmness, function and symmetry, Device palpability (baseline assessment excluded), Mass formation, Cheek sensation as well as visual function assessments.

Information on AEs can also be obtained from signs and symptoms detected during each examination by the Investigator or designee, which should include visual inspection of the treatment area. AEs must be documented in the source document and eCRF without regard for cause or relation to investigational product. Events that occur after Screening but prior to randomization should be recorded in the subject's medical history.

If in the process of the interview, additional information regarding medical history or pre-planned medical or surgical procedures is revealed, it must be documented in the source document(s) and the eCRF.

It is the responsibility of the Treating Investigator to determine severity of the AE and relatedness of the event to the study product and/or injection procedures. Adverse Events must be reported as outlined below in section 8.6.

8.1 Assessment of AEs by direct questioning to subject and evaluation of subject

Each subject should be questioned about AEs at each visit following randomization and/or treatment. Definition and Reporting requirements are found in section 8.6.

8.2 Subject Diary Data

A subject diary will be dispensed to all subjects for daily completion for 28 days beginning on injection day for each treatment with direct questioning for pain, tenderness, redness, bruising, swelling, itching, lumps/bumps and "other".

The subject will also be specifically instructed to record presence of any of the following symptoms in the "other" section; Changes in vision (i.e. loss of vision, blurriness, double vision, pain in or around your eye, blindness, blind spots, problems moving your eyes), Skin changing color around the eyelids, Crusty or scabby skin around the eyelids, Pain, Headache, Fever, Dizziness, Confusion, Weakness or numbness in the arms or legs, Changes to consciousness or alertness, Difficulty speaking/ speech impairment or Face droop. The diary will include specific instructions to seek immediate medical attention if any of these symptoms or signs are observed.

Diary data will be counted and displayed separately from other AE data.

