	□ Inferior border - from medial border at mandibular ramus to angle of mandibular ramus
	□ Lateral border - from angle of mandibular ramus to top of tragus
Effectiveness Assessment(s):	1. Cheek wrinkles by Blinded Evaluator using
	2. Cheek wrinkles by Treating Investigator using
	3. Global aesthetic improvement by Treating Investigator and Subject using GAIS.

	4. Improvement in cheek wrinkles by Central Independent Photographic Reviewer.
	5. Subject's satisfaction after treatment using a Subject Satisfaction Questionnaire.
	6. Subject's satisfaction using FACE-Q "Satisfaction with Cheeks".
	7. Lifting effect of cheek using 3D imaging
	8. Return to social engagement after treatment using subject diaries.
	9. Dermal thickness using Ultrasound.
	10. Radiance, skin tightness and jawline contour assessed live by Treating Investigator.
Safety Assessment(s):	1. Adverse Event reporting: AEs will be obtained from signs and symptoms reported by the subjects or detected during each examination
	2. A subject diary will be dispensed to all subjects in the treatment group for daily completion for 28 days beginning on injection day for each treatment with direct questioning for pain, tenderness, redness, bruising, swelling, itching, lumps/bumps and "other". Subjects will be specifically asked to record any of the following symptoms in the other section; changes in vision (i.e. loss of vision, blurriness, double vision, pain in or around your eye, blindness, blind spots, problems moving your eyes), skin changing color around the eyelids, crusty or scabby skin around the eyelids, pain, headache, fever, dizziness, confusion, weakness or numbness in the arms or legs, changes to consciousness or alertness, difficulty speaking/ speech impairment and face droop.
	3. Functionality, sensation, firmness, symmetry, mass formation and palpation tests according to pre-defined methods, at baseline and at each on-site follow-up visit.
	4. Device deficiencies will be assessed at treatment visits.
	5. Visual function assessments will be performed before and 30 minutes following injection and at all scheduled follow up visits.

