2.4 Risks and benefits

Anticipated benefits for subjects treated with Sculptra Aesthetic for the correction of cheek wrinkles include restoration of a more youthful appearance, relatively long-lasting effects which would reduce the need for frequent touch-up procedures. The benefit of Sculptra Aesthetic for correction of cheek wrinkles is being evaluated in the ongoing, post-approval US clinical study (US10321). (4) Although treatment in the cheek area was secondary to treatment in the nasolabial folds in this study, the interim data results support that treatment for cheek wrinkles is effective and well tolerated.

Since the initial approval of Sculptra Aesthetic in 1999 (EU), the amount of SWFI used to reconstitute Sculptra Aesthetic has gradually increased. Based on medical literature and physician experience, practitioners have reported improved clinical outcomes with increased reconstitution volumes that are up to two times higher than the volume recommended by the manufacturer and usually in combination with anesthetic solutions, like lidocaine 2%. (3, 5) It has also been suggested, that a reduction in frequency of nodules/papules can be achieved with an increased reconstitution volume. (6, 7). Currently, the increased reconstitution volume for treatment of nasolabial folds is evaluated in the ongoing study 43USSA1705.

Risks with Sculptra Aesthetic as with any other injectable implant include infections, perforation of blood vessels, trauma to nerves and lumps. The most common reported adverse events (AEs) after Sculptra Aesthetic treatments are formation of papules and nodules, swelling, mass/induration, of which most resolve with time.

Infection, and damage to body structures such as nerves or blood vessels at the injection site, have also been reported. Rare but serious AEs associated with the intravascular injection of soft tissue fillers in the face have been reported and include temporary or permanent vision impairment, blindness, cerebral ischemia or cerebral hemorrhage, leading to stroke, skin necrosis, and damage to underlying facial structures.

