 $\hfill\square$ Superior border - from top of tragus to top of alar crease

 $\hfill\square$ Medial border - from top of the alar crease, along the NLF to the inferior border of the mandibular ramus

 $\hfill\square$ Inferior border - from medial border at mandibular ramus to angle of mandibular ramus

 $\hfill\square$ Lateral border - from angle of mandibular ramus to top of tragus

Injection technique

The injection technique is important for the aesthetic effect of the treatment. It is recommended to use a standard injection technique for all subjects per site to limit variability due to technique. Before product is injected, aspiration should be done to avoid intravascular injection.

The injection technique is at the discretion of the investigator, proposed techniques are:

- Antegrade linear threading: also called push-ahead technique as some product is pushed ahead of the needle. Once the needle is in place, the product is injected ahead while inserting the needle in the tissue.
- Retrograde linear threading: the needle is threaded into the tissue at the appropriate depth, and the product in injected as a straight line on withdrawal of the needle
 - Bolus: multiple aliquot injections of the product is injected along a line or regions of the tissues
- Fanning: a number of linear threads to spread the product over a wider area
- Cross-hatching: combines multiple injections of linear threading that crisscross at right angle to provide volume in a square shape

6.5.2 Treatment regimen (dose and interval)

Eligible subjects randomized to the treatment group will receive a single regimen of Sculptra Aesthetic. A single regimen consists of up to 4 injection sessions with 1-month (+5 weeks) intervals. The first treatment will be administered on Day 1/ Baseline visit. Sufficient amount of study product, as determined by the Treating Investigator, should be injected to achieve optimal correction:

□ Optimal correction is defined as at least a one-step improvement on the

t and the best correction that can be achieved as agreed by Treating Investigator and subject.

□ Three additional treatment sessions may be performed if needed to achieve optimal correction, as determined by the Treating Investigator and subject.

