#### 1.3.6 Subject Diary

A subject diary will be dispensed to all subjects in the Treatment Group for daily completion for 28 days beginning on injection day for each treatment with direct questioning for pain, tenderness, redness, bruising, swelling, itching, lumps/bumps and "other". Subjects will be specifically asked to record any of the following symptoms in the other section: changes in vision (i.e. loss of vision, blurriness, double vision, pain in or around your eye, blindness, blind spots, problems moving your eyes), skin changing color around the eyelids, crusty or scabby skin around the eyelids, pain, headache, fever, dizziness, confusion, weakness or numbness in the arms or legs, changes to consciousness or alertness, difficulty speaking/speech impairment and face droop.

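### The diary's urgent-care list limits crusting and skin colour change to the eyelids; crusting of the injected cheek is not named, and unusual cheek colour is not tied to the instruction

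*Protocol*

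**What the plan says.** Protocol section 8.2 gives the diary two lists. The first is asked about by name each day for 28 days from each injection: "direct questioning for pain, tenderness, redness, bruising, swelling, itching, lumps/bumps", plus an open item for anything else. The second is a set of signs that subjects are told to record under that open item. It covers visual, neurological and general symptoms and two skin signs: "Skin changing color around the eyelids, Crusty or scabby skin around the eyelids". The paragraph with the second list ends: "The diary will include specific instructions to seek immediate medical attention if any of these symptoms or signs are observed".

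The synopsis, under safety assessments, has the same eyelid restriction ("skin changing color around the eyelids, crusty or scabby skin around the eyelids, pain, headache, fever"), and so does SAP 1.3.6 ("skin changing color around the eyelids, crusty or scabby skin around the eyelids"). Neither repeats the urgent-care instruction.

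The upper edge of the treatment area is set in section 6.5.1: "Superior border - from top of tragus to top of alar crease". Section 2.4 describes rare but serious consequences of intravascular injection in the face, ending with "leading to stroke, skin necrosis, and damage to underlying facial structures". Necrosis is not limited there to any part of the face.

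Section 6.5.3 sends the reader elsewhere for the full advice to subjects: "Detailed information regarding the post-treatment care and patient instruction is provided in the study IFU".

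**The concern.** The protocol treats crusting and colour change as urgent near the eye, yet the skin that receives the product is the cheek, and the eyelids lie above the upper border of the treated area. Section 2.4 recognises skin necrosis as a serious risk, and section 8.6.8 makes necrosis from a vascular embolic event a reason to halt a site. A list built as this one is would be expected to name the same signs on the injected skin.

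What is at stake is the individual subject. Someone who sees scabbing or an unusual colour on the cheek, and reads a list naming only the eyelids, may wait instead of calling. The possible harm is delayed attention. The effectiveness and safety analyses would be unaffected.

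**Working it through.** There is no figure in the plan to reproduce. The check is a reading of the lists with simple counts.

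**Urgent list, section 8.2**

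| Group | Items | Count |
|---|---|---|
| Vision | visual changes | 1 |
| Skin | colour change; crusting or scabbing | 2 |
| General | pain; fever; headache | 3 |
| Neurological | dizziness; confusion; limb weakness or numbness; altered alertness; speech difficulty; facial droop | 6 |

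Total: 1 + 2 + 3 + 6 = 12. Both skin items are limited to the eyelids (2 of 2), and neither names the treated area (0 of 2). Pain is listed without a site.

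**Symptoms asked about daily by name, section 8.2**

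There are seven. Redness and bruising describe ordinary colour change (2 of 7). None describes crusting or scabbing (0 of 7).

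**The two lists set against the treated cheek**

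| Cheek sign | Asked daily by name | On the urgent list |
|---|---|---|
| Ordinary redness or bruising | yes | no, and reasonably so |
| Colour change beyond that | no | no (eyelids only) |
| Crusting or scabbing | no | no (eyelids only) |

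**Which list the instruction covers.** It closes the paragraph containing the 12 items, so its natural reach is those items. Extending it to the first list would send every subject with expected redness or bruising for urgent care, and cheek crusting would still be unnamed.

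**Timing, for context only.** The telephone call falls at 72 ± 24 hours, that is 72 − 24 = 48 to 72 + 24 = 96 hours after injection. With injection day as day 1, this is diary day 3 to day 5. Diary days left after the call are 28 − 3 = 25 to 28 − 5 = 23. The next treatment visit is one month (+5 weeks) after the injection, with a month defined as 4 weeks, so 4 to 4 + 5 = 9 weeks. For most of the diary period the diary is therefore the only daily structured prompt. This does not measure any delay in care.

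**The case against.** The strongest reply is that the texts actually given to subjects were not available. Section 8.2 only describes what the diary will contain, section 6.5.3 places detailed patient instructions in the IFU, and the Intravascular Treatment Protocol is a separate document. Any of these could hold a cheek warning. This stands in full: the finding is about the wording of the protocol and SAP, and it makes the fix conditional.

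A second reply is that the list was meant for visual and neurological emergencies, with local reactions left to the direct questions. That may explain the eyelid wording. But the direct questions do not include crusting, and the lists are not cleanly separated by purpose, since pain is on both.

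Third, neither document says that cheek crusting or colour change warns of necrosis. That is correct. However, the protocol itself calls for immediate attention when these signs appear near the eye, and it names necrosis as a risk of injection in the face. That is enough to ask why the injected skin is left out.

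Fourth, other safeguards exist:

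- aspiration before injection;
- a pre-treatment briefing on risks and when to call the investigator;
- adverse event evaluation by the treating investigator on each treatment day;
- the 72-hour call, which also reviews diary events;
- unscheduled visits;
- visual inspection of the treatment area at examinations (section 8);
- the open diary item, and pain with no site limit on the urgent list.

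These reduce the risk and keep the point modest. None supplies a named daily prompt for the treated skin, and pain helps only the subject who has it.

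Finally, the colour gap is narrower than the crusting gap, because ordinary redness and bruising are already asked about and should stay off an urgent list. That also stands, and it is why the colour item needs medical wording.

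**Conclusion.** The concern holds as a statement about the protocol and SAP text. Both skin signs on the 12-item urgent list are confined to the eyelids. Cheek crusting appears in neither list, and cheek colour change beyond expected redness or bruising is not linked to urgent care.

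Its practical weight depends on one unverified assumption: that neither the diary form nor the IFU already warns subjects about the cheek. The documents give no necrosis rate or onset time, so the size of the harm cannot be estimated. No endpoint, analysis or stopping rule changes. It is a change that should be made on subject-safety grounds if the check of those two documents finds no warning; confidence is medium.

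**What to change.** First check whether the diary form or the IFU already tells subjects to seek care for crusting or unusual colour of the cheek. If either does, the protocol wording need only be aligned with it.

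If neither does, make two changes in section 8.2, the synopsis and the diary form:

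1. Extend the crusting item so that it applies to the eyelids or the treated area.
2. Leave the eyelid colour item alone and add a separate item for colour change in the treated area, worded by the medical expert to exclude expected redness and bruising. Skin turning white, grey, dusky or blotchy is one possible wording.

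Amend SAP 1.3.6 for consistency only: SAP 2.5.2 tabulates the expected symptoms and specifies no analysis of these two items.

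The cost is small but more than a single phrase. One item is extended, one new item needs medical input, and section 12.3 requires a written amendment. Some subjects will make contact about harmless skin changes. Only treatment sessions still to be given would benefit, and the documents do not say how many remain.

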8.3 Laboratory assessments

For all women of childbearing potential, including those currently using contraception, a urine pregnancy test will be performed at screening and all injection visits (prior to treatment). The test result must be negative for the subject to receive any treatment with study product. The test result will be documented in source data and the eCRF.

8.4 Visual Function assessments

Visual function assessments will be performed for all subjects. For subjects in the treatment group, the assessments will be performed both prior to and post injection of the study product at baseline and all scheduled treatment visits. The post-treatment assessments should be performed 30 min after the injections are completed. In the event of blindness or any significant ophthalmic sign or symptom,

subjects are to undergo immediate evaluation by an ophthalmologist or a retina specialist. All incidences of visual disturbances, regardless of relationship to study product or seriousness, are considered Adverse Events of Special Interest (AESIs) and include but are not limited to the following: any loss of vision, blurry vision, double vision, pain in or around the eye, blind spot or shadow in the visual field, trouble moving eyes. AESI's should be reported (using the Adverse Event Clarification Form) within 24 hours of awareness. Please refer to recording instructions in section 8.6.6.

8.4.1 Snellen visual acuity test

A Snellen Eye Chart will be used to assess visual acuity for distance vision. Visual Acuity will be conducted using the subject's best distance correction (e.g. with contacts or spectacles) at a distance of 6 feet from the chart. Each eye will be measured separately by either using an occluder or having the subject cover one eye at a time. The subject will be asked to start reading the letters at the top of the chart working their way to the bottom. The smallest row of letters that the subject can read will indicate their visual acuity listed on the chart. Snellen Visual Acuity will be recorded in their source documentation and eCRF. If there are two or more visual acuity line changes during the course of study, these should be reviewed and assessed by the Investigator for a potential adverse event.

